10.1.2 Analysis details

Both co-primary endpoints will be analysed by means of MI-RD to handle missing data. Retrieved drop-out patients are defined as patients who discontinue study treatment and decide to remain in the study by following the schedule of assessments and continuing to adhere to protocol requirements. Consequently, for each primary endpoint, MI will be performed based on the subjects' allocated treatment arm and observed values (baseline and intermediate) as covariates in a regression model using data from Retrieved drop-out patients that have the primary endpoint assessment done.

# 10.1.2.1 Schirmer I test >10mm/5min at week 4

This primary endpoint will be analyzed by means of a logistic regression model adjusting by predefined baseline factors (gender, age class, baseline Schirmer I test value as fixed effects and site as random effect) and a one-sided test will be used to test for differences between treatment groups.

For the imputation of missing data of Schirmer I test, a regression model will be created by including the baseline Schirmer I test value, gender, age class, and Schirmer I test at week 2. Two hundred data sets will be generated, and the random seed number will be 180404. MI will be implemented in the following steps:

1. Partial imputation assuming Missing at Random (MAR) will be carried out to impute intermittent (non-monotone) missing data of Schirmer I test up to week 4 based on a

multivariate joint Gaussian imputation model using the Markov chain Monte Carlo (MCMC) method. A separate imputation model will be used for each treatment arm. In case of non-convergence or non-estimability issues, a single imputation model will be considered (with treatment arm added as explanatory variable to the model). A total of 200 datasets will be created. These datasets will be utilized in Step #2.

- 2. The remaining monotone missing data will be imputed using a MI regression including the same explanatory variables of the previous step. According to MI-RD approach, only non-missing values from retrieve dropouts will be used to inform the regression model.
- 3. Each of the 200 imputed datasets will be analyzed using observed and imputed data. Rubin's rule will be used for combining results to draw inference.

If there are not enough retrieved dropouts for convergence of MI-RD regression model, a referencebased Multiple Imputation (MI) approach will be adopted to consider a missing not at random (MNAR) mechanism for missing data: imputation of values in the rhNGF arm (above step #2) will be done using the non-missing values from the control group (this approach will be referred as "Copy Reference"). This approach does not assume benefits for rhNGF in case of discontinuation and limits a post-discontinuation clinical effect to that of vehicle. The final decision on the use of the MI-RD vs Copy-Reference for this endpoint will be done at the time of the analysis and reported in the CSR.

Whether for MI-RD or Copy-Reference approach, the adjusted estimated treatment differences in proportions between cenegermin and vehicle at week 4 will be displayed together with the corresponding two-side 95% confidence intervals and p-value.

### 10.1.2.2 Change from baseline in the global SANDE score at week 12

This co-primary endpoint will be analyzed by means of an Analysis of Covariance (ANCOVA) adjusting by pre-defined baseline factors (gender, age class, baseline global SANDE score as fixed effects and site as random effect) and a one-sided test will be used to test for differences between treatment groups. Rules for derivation of SANDE scores are reported in section 12.2.

For the imputation of missing data, a regression model will be created by including the baseline global SANDE score, gender, age class, and intermediate global SANDE scores up to week 12. Two hundred data sets will be generated, and the random seed number will be 252404. MI will be implemented in the following steps:

- 1. Partial imputation assuming MAR will be carried out to impute intermittent (non-monotone) missing data of global SANDE score based on a multivariate joint Gaussian imputation model using the MCMC method. A separate imputation model will be used for each treatment arm. In case of non-convergence or non-estimability issues, a single imputation model will be considered (with treatment arm added as explanatory variable to the model). A total of 200 datasets will be created. These datasets will be utilized in Step #2.
- 2. The remaining monotone missing data will be imputed using a MI regression including the same explanatory variables of the previous step. According to MI-RD approach, only non-missing values from retrieve dropouts will be used to inform the regression model.
- 3. Each of the 200 imputed datasets will be analyzed using observed and imputed data. Rubin's rule will be used for combining results to draw inference.

If there are not enough retrieved dropouts for convergence of MI-RD regression model, a Copy Reference approach will be adopted to consider a MNAR mechanism for missing data. The final decision on the use of the MI-RD vs Copy-Reference for this endpoint will be done at the time of the analysis and reported in the CSR.

Whether for MI-RD or Copy-Reference approach, the adjusted estimated treatment differences in means for global SANDE score between cenegermin and vehicle at week 12 will be displayed together with the corresponding two-side 95% confidence intervals and p-value.

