Screening visit	Day -8	
 
The following procedures will be performed (order below is mandatory):
 
Explanation to the patient of study aims, procedures and possible risks
 
Informed consent signature
 
Screening number allocation
 
Patient eligibility: Inclusion/exclusion criteria evaluation
 
Pregnancy test for female patients of childbirth potential
 
Demographic data
 
Ocular and systemic medical history
 
Previous and concomitant ocular and systemic medications (prior to start the study)
 
Ocular examination of both eyes, to be performed by the physician investigator: 
 
Assessment by SANDE questionnaire
 
Assessment of best corrected distance visual acuity (BCDVA)
 
External Ocular Examination
 
Schirmer test I (without anesthesia)
 
Slit-lamp examination (SLE) to assess the eyelid (Meibomian glands), eyelid (erythema), eyelid (edema), lashes, conjunctiva erythema, lens, iris, anterior chamber, corneal horizontal diameter
 
TFBUT
 
Ocular surface staining (NEI score - corneal and conjunctival fluorescein staining)
 
AE collection
 
Preservative free artificial tears dispensation
 
The Investigator will dispense to the patients the preservative free artificial tears (Blink® Tears or equivalent), provided by Sponsor, to be used only if strictly needed by the patient (the patient must follow the instruction in the product leaflet). The patients will be instructed to enter information of self-administration of Blink® Tears or equivalent (for each administered dose and AE occurrence into the diary. The diary will be given from the PI or delegate during this visit
 
 
 

At home	Day -8 – Day 1+2 (baseline)	
 
Recording any unusual medical conditions - AE monitoring (diary)
 
Artificial tears use during the wash-out period (diary)
 
Data will be recorded by the patient on the patient's diary.
 

	Day	Procedures/Assessments

		The following procedures will be performed (order below is mandatory):

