## 9.4.3. Analysis of efficacy variables

## 9.4.3.1. Primary analyses

The following null hypothesis is defined on the first primary endpoint: the proportion of patients reaching a value of Schirmer I test (without anesthesia) >10mm/5min at week 4 in cenegermin (rhNGF) is lower or equal than control:

 $H_{01}: T_{rhNGF} \leq T_{CONTROL}$ 

 $H_{11}: T_{rhNGF} > T_{CONTROL}$ 

where  $T_{rhNGF}$  and  $T_{CONTROL}$  are the proportion of patients reaching a value of Schirmer I test (without anesthesia) >10mm/5min at week 4 for cenegermin and control groups, respectively. The null hypothesis  $H_{01}$  will be rejected if the associated primary analysis p-value will be lower than 0.025.

This primary endpoint will be analyzed by means of a logistic regression adjusting by pre-defined baseline factors (site, gender, age class, baseline Schirmer I test value) and a one-sided test will be used to test for differences between treatment groups.

Similarly, the following null hypothesis is defined on the co-primary endpoint: the change from baseline in the global SANDE score at week 12 in cenegermin is lower or equal than control:

 $H_{02}:\,\mu_{rhNGF} \leq \mu_{CONTROL}$ 

 $H_{12}: \mu_{rhNGF} > \mu_{CONTROL}$ 

where  $\mu_{rhNGF}$  and  $\mu_{CONTROL}$  are the change from baseline in the global SANDE score at week 12 for cenegermin and control groups, respectively. The null hypothesis H02 will be rejected if the associated primary analysis p-value will be lower than 0.025.

This co-primary endpoint will be analyzed by means of an ANCOVA model adjusting by pre-defined baseline factors (site, gender, age class, baseline global SANDE score) and a one-sided test will be used to test for differences between treatment groups.

Both null hypotheses H01 and H02 must be rejected in order to claim superiority of cenegermin over control. Consequently, no multiplicity correction of type I error will be applied on primary endpoints analysis.

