# 5. Sample size justification

The sample size of the study is calculated based on results from previous studies.

Sample size was calculated according to the following assumptions:

- randomization ratio 1:1.
- a difference of 42% in Schirmer I rate of responders (value >10mm/5min at week 4.) in favor of rhNGF treatment at Week 4, with a responder rate of 33% for vehicle.
- 10 points in Global SANDE score improvement at Week 12, with a standard deviation of 12 points.

Based on these assumptions, a total sample size of 72 evaluable patients (80 pts considering 10% of patients not evaluable after enrollment) allows to achieve an overall power of 90% to show superiority of rhNGF eye drops solution vs vehicle in terms of primary endpoint, considering a one-sided alpha of 0.025.

Specifically:

- A power of 96.3% is achieved for Schirmer I primary endpoint.
- A power of 94.1% is achieved for SANDE primary endpoint.

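### The SANDE co-primary ANCOVA is valid but leaves out the screening SANDE score and splits age at the median; adding both is a nearly free, probably modest, gain in precision

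*SAP*

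**What the plan says.** Protocol 6.1 lists "Assessment by SANDE questionnaire" among the procedures at the screening visit (day -8) and again at Visit 1, where it comes before the eligibility check and randomisation. A global SANDE score above 25 mm is an entry criterion in the synopsis, and the schedule of evaluations has eligibility reviewed at both visits.

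SAP 4.5 takes Visit 1 as baseline. The protocol (9.4.3.1) specifies the SANDE ANCOVA as "adjusting by pre-defined baseline factors (site, gender, age class, baseline global SANDE score". SAP 10.1.2.2 keeps the same covariates with site as a random effect: "adjusting by pre-defined baseline factors (gender, age class, baseline global SANDE score as fixed effects and site as random effect". The code in SAP 15.4.2 carries a single pre-treatment SANDE value and a two-level age variable whose reference level is at or below the median. SAP 8.4 shows that age is also held in years. SAP 10.2.2.2 and 10.2.2.3 apply the same model to SANDE severity and frequency.

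The imputation model in 10.1.2.2 uses baseline SANDE, gender, age class and the intermediate scores; the variable lists in 15.4.2 name weeks 2, 4 and 8. Screening SANDE appears in neither the analysis model nor the imputation model.

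**The concern.** A single visual-analogue reading is noisy. A second reading of the same scale, also taken before randomisation, can be added as a covariate without biasing the comparison, and it reduces residual variance to the extent that it predicts week 12 beyond what baseline already tells us. Splitting age at the median discards part of whatever age explains.

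Both co-primary null hypotheses must be rejected, and SANDE has the lower stated power of the two (94.1% against 96.3%, SAP 5). Protocol 9.1 calls the 10-point difference ambitious. Precision on this endpoint is therefore worth having if the true effect is smaller, and these data are already being collected.

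**Working it through.** **Inputs from SAP 5.** "10 points in Global SANDE score improvement at Week 12, with a standard deviation of 12 points"; "randomization ratio 1:1"; "a total sample size of 72 evaluable patients (80 pts considering 10% of patients not evaluable after enrollment"; "considering a one-sided alpha of 0.025". That gives 36 evaluable patients per arm.

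**The plan's own figure.** The claim is "A power of 94.1% is achieved for SANDE primary endpoint". The standard error is 12 × √(2/36) = 2.83, and 10/2.83 = 3.54. Normal approximation: Φ(3.54 − 1.96) = 94.2%. Noncentral t with 70 df: 93.7%. The stated figure reproduces and takes no credit for covariates.

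**Adding the screening score.** Let b be the baseline–week 12 correlation, s the screening–week 12 correlation and c the screening–baseline correlation. The documents give none of these, so all values below are assumptions.

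- Residual variance with baseline only: 1 − b².
- With both scores: 1 − R², where R² = (b² + s² − 2bsc)/(1 − c²). If s = b, this reduces to R² = 2b²/(1 + c).
- Variance ratio = (1 − R²)/(1 − b²); equivalent sample size = 72/ratio.

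Worked case, c = 0.7 and b = s = 0.5: R² = 0.50/1.70 = 0.294; ratio = 0.706/0.75 = 0.941. Variance falls 5.9%, the confidence interval narrows by 3.0%, and 72/0.941 = 76.5, a gain of 4.5 patients.

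| c | b | s | Fall in variance | Equivalent N (from 72) |
|---|---|---|---|---|
| 0.6 | 0.6 | 0.6 | 14.1% | 83.8 |
| 0.7 | 0.5 | 0.5 | 5.9% | 76.5 |
| 0.8 | 0.4 | 0.4 | 2.1% | 73.6 |
| 0.7 | 0.5 | 0.45 | 2.6% | 73.9 |
| 0.7 | 0.5 | 0.40 | 0.7% | 72.5 |
| 0.7 | 0.5 | 0.35 | 0% | 72.0 |

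The first three rows assume that screening predicts week 12 as well as baseline does. The last three relax that. The gain is exactly zero when s = b × c (0.5 × 0.7 = 0.35), because screening then carries no information beyond baseline.

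**Effect on power.** Taking 12 as the residual SD of the planned model (an assumption), the 5.9% case moves power from 93.7% to 94.9% at a 10-point difference, and from 68.5% to about 71% at 7 points.

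**Age in years.** For a normally distributed covariate with a linear effect, a median split keeps 2/π = 64% of the variance it explains. If age explains 5%, the ratio is (1 − 0.05)/(1 − 0.05 × 0.637) = 0.950/0.968 = 0.981, a fall of 1.9%. It is smaller if age explains less.

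**The case against.** The strongest reply is that nothing here is an error. ANCOVA on the last pre-dose value is standard, and the protocol and SAP agree on the covariates. That stands: this is an efficiency suggestion. A reader might infer from the lower SANDE power that the plan is underpowered or biased. The documents do not support that, because the stated power reproduces without any help from covariates, and a median split of age made without reference to treatment or outcome introduces no bias.

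The second reply concerns size, and it also stands. It is tempting to treat the two scores as replicates and promise at least a 2% gain. Other topical treatments, lenses and plugs stop at screening (protocol 3.3 and exclusion criteria 11 and 12), so the screening score may reflect conditions that no longer hold. Baseline and week 12 are both scheduled with those treatments excluded, and baseline is closer to week 12 in time. The lower bound is therefore zero. In the other direction, setting all three correlations at 0.8 would give 20%, but that requires week 12 to track baseline as closely as two readings 8 to 10 days apart.

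Two further readings go too far. One is that the imputation ignores everything except baseline; SAP 10.1.2.2 includes the intermediate scores. The other is that eligibility guarantees both readings; they are scheduled, but SAP 8.8.2 itself plans to report baseline SANDE assessments that were not done.

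Finally, the monotone imputation step is fitted on retrieved drop-outs only, and the SAP already allows for too few of them. With about 8 of 80 patients expected to be non-evaluable, another predictor there could make convergence harder. This is a reason for care in that step and does not affect the ANCOVA change.

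**Conclusion.** The point holds as an optional improvement at low cost. The planned analysis is valid. It leaves unused a pre-randomisation SANDE score that is already scheduled, and it coarsens age without need. The expected benefit is a fall in residual variance of about 0 to 14%, with 6% (4 to 5 patients on a base of 72) as an illustrative middle case, plus under 2% from age if age explains up to 5%. The upper part of the range assumes a screening–baseline correlation of 0.6 to 0.8, a correlation of 0.4 to 0.6 with week 12, and equal predictive value for the two scores. The zero end applies if the pre-wash-out score adds nothing. Most of any gain would come from screening SANDE rather than age. None of the correlations is documented, so the direction is firmer than the size.

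**What to change.** By SAP amendment before database lock and unblinding:

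- Add screening global SANDE as a second covariate in the 10.1.2.2 ANCOVA, and the matching screening score in 10.2.2.2 (severity) and 10.2.2.3 (frequency).
- Keep Visit 1 as the reference for change, so that endpoint and estimand are unaltered.
- Enter age in years in place of age class in these models.
- Add screening SANDE to the MCMC step for intermittent missing data. Add it to the retrieved-drop-out step only if that model remains estimable. The regression line for that step in 15.4.2 names only treatment, age and sex, which is narrower than the text of 10.1.2.2, so reconcile the two while amending the code.
- Fill any missing screening score beforehand by a simple stated rule that does not use treatment assignment, since the MCMC step is run separately by arm.
- List the change in SAP 7.9 as a departure from the covariates in protocol 9.4.3.1.

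The cost is one degree of freedom for the screening score, none for age (one term replaces another), and the amendment to the SAP and code. No extra visits, patients or data collection are needed.

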# 10.1.3 Sensitivity analyses

The following sensitivity analyses are defined to assess the robustness of results on each primary endpoint versus assumptions used in the statistical model for the main estimators:

- The comparison between treatment and control will be performed by means of MI under MAR assumption instead of MNAR. MI will be implemented in two steps:
  - Intermittent missing data up to primary time point (Week 4 for Schirmer I test, and Week 12 for SANDE) will be imputed using MCMC methods assuming MAR. A separate imputation model will be used for each treatment arm. The imputation models will include the observed values (baseline and intermediate), gender, and age class as covariates. In case of non-convergence or non-estimability issues, a single model will be considered with treatment arm added as explanatory variable to the model.
  - The remaining missing values with a monotone missing data pattern will be imputed based on data of corresponding treatment group.
  - Each imputed dataset will be analyzed using observed and imputed data. Rubin's rule will be used for combining results to draw inference. The adjusted estimated treatment differences between cenegermin and vehicle (difference in proportions for Schirmer's test and differences in means for SANDE) will be displayed together with the corresponding two-side 95% confidence intervals and p-values.
- A tipping point strategy will be used as a sensitivity analysis for missing data for assessment of superiority (if shown) of rhNGF for each endpoint. Tipping point analysis will assess how departures from MI under MNAR assumptions must be to overturn conclusions from the primary superiority analysis. Tipping point will be based on iterative application of MI. In the first iteration, MI-RD method is assumed as described in section 10.1.2. In successive iterations, the imputed values for the rhNGF arm are shifted by a constant to represent a worse effect in each iteration. This can be achieved by using the N completed datasets obtained under MI-RD and shift the imputed values. The tipping point is the shift at which the p-value becomes non-significant. Outline of tipping point:
  - Use MI-RD to impute missing values.
  - Assuming that the tipping point is between -10 and 0, the following actions will be performed for  $\Delta = 0, -0.1, -0.2, -0.3, \dots, -10$ :
    - Add  $\Delta$  to the imputed values at the rhNGF arm.
    - Analyze the completed data sets using the same method outlined in section 10.1.2.
    - the plot of all p-values for  $\Delta$  between -10 and 0 will be created.
  - $\circ$  based on the plot, the approximate value of the tipping point Tpapprox is identified considering a threshold for the p-values of 0.02500.
  - after identification of  $Tp_{approx}$ , finest research of the tipping point will be performed in the range  $Tp_{approx} \pm 1$  by incrementing  $\Delta$  of 0.01 and following the usual steps:
    - Add  $\Delta$  to the imputed values at the rhNGF arm.
    - Analyze the completed data sets using the same method outlined in section 10.1.2.
  - The tipping point is the smallest  $\Delta$  at which p-value  $\geq 0.02500$ .

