## 9.4.3.2. Sensitivity analyses

The following sensitivity analyses are defined to assess the robustness of results on each primary endpoint versus assumptions used in the statistical model for the main estimators:

- The comparison between treatment and control will be performed in the FAS population by means of MI under MAR assumption instead of missing not at random (MNAR). MI will be implemented in two steps:
  - Intermittent missing data up to primary time point (week 4 for Schirmer I test and week 12 for SANDE) will be imputed using MCMC methods assuming MAR. A separate imputation model will be used for each treatment arm. The imputation models will include the observed values (baseline and intermediate), gender, and age class as covariates. In case of nonconvergence or non-estimability issues, a single model will be considered with treatment arm added as explanatory variable to the model;
  - The remaining missing values with a monotone missing data pattern will be imputed based on data of corresponding treatment group.

Each imputed dataset will be analyzed using observed and imputed as described in section 9.4.3.1. Rubin's rule will be used for combining results to draw inference. The adjusted estimated treatment differences between cenegermin and vehicle (difference in proportions for Schirmer I test and differences in means for SANDE) will be displayed together with the corresponding two-side 95% confidence intervals and p-values.

A tipping point strategy will be used as a sensitivity analysis for missing data for assessment of superiority (if shown) of cenegermin. Tipping point will assess how departures from MI under MNAR assumptions must be in order to overturn conclusions from the primary superiority analysis. Tipping point will be based on iterative application of MI-RD (or MI under wash-out approach), where the imputed values for the cenegermin arm are shifted at a constant Δ to represent a worse effect in each iteration. The tipping points are the smallest Δs at which no statistical significance is shown (p≥0.025).

In addition, for each co-primary endpoint, the regression models detailed in section 9.4.3.1 will be performed for supportive purposes:

- by considering complete cases only (i.e. without considering patients with missing primary endpoint);
- on the PP set instead of FAS.

Details on sensitivity and supportive analyses will be provided in the SAP.

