# **10.** Evaluation of Efficacy

# 10.1 Analysis of primary efficacy endpoint

10.1.1 Testing strategy and multiplicity adjustment

The following null hypothesis is defined on the first primary endpoint: the proportion of patients reaching a value of Schirmer I test (without anesthesia) >10mm/5min at week 4 in cenegermin (rhNGF) is lower or equal than control:

H01:  $T_{rhNGF} \leq T_{CONTROL}$ 

H11: TrhNGF > TCONTROL

where  $T_{rhNGF}$  and  $T_{CONTROL}$  are the proportion of patients reaching a value of Schirmer I test (without anesthesia) >10mm/5min at week 4 for cenegermin and control groups, respectively. The null hypothesis  $H_{01}$  will be rejected if the associated primary analysis p-value will be lower than 0.025.

Similarly, the following null hypothesis is defined on the co-primary endpoint: the change from baseline (reduction) in the global SANDE score at week 12 in cenegermin is lower or equal than control:

H02:  $\mu_{rhNGF} \leq \mu_{CONTROL}$ 

H12:  $\mu_{rhNGF} > \mu_{CONTROL}$ 

where  $\mu_{rhNGF}$  and  $\mu_{CONTROL}$  are the change from baseline (reduction) in the global SANDE score at week 12 for cenegermin and control groups, respectively. The null hypothesis H02 will be rejected if the associated primary analysis p-value will be lower than 0.025.

Both null hypotheses  $H_{01}$  and  $H_{02}$  must be rejected to claim superiority of cenegermin over control. Consequently, no multiplicity correction of type I error will be applied on primary endpoints analysis.

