# **12.2 SANDE derivation**

The SANDE questionnaire is comprised of two questions:

- How often do your eyes feel dry and/or irritated?
- How severe you feel your symptoms of dryness and/or irritation are?

This questionnaire uses a 100 mm horizontal line for each question to assess ocular discomfort and/or dryness experienced by the patients. In the SANDE questionnaire, frequency of symptoms ranges from "rarely" to "all of the time" and the severity of symptoms ranges from "very mild" to "very severe". Patients are asked to place a mark on the two given lines based on the extent of their symptoms.

The locations of the marks made by the patients on the 100 mm horizontal lines will be measured in mm from left to right and recorded as frequency and severity score, respectively.

The global SANDE score will be calculated by multiplying the frequency score by the severity score and obtaining the square root.

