# 15.3 Figures

| Number - Title - Population   | KFR | Final analysis |
|---|-----|----------------|
| Figure 14.1.3.2 Time from randomization to discontinuation (Kaplan-Meier) . Randomized set  |     | x              |
| Figure 14.2.3.5 Tipping point Shirmer test. Full analysis set   |     | x              |
| Figure 14.2.3.6 Tipping point plot SANDE. Full analysis set   |     | x              |
| Figure 14.2.5.1.1 Schirmer I test Observed Mean (±SEM) at each timepoint. Full analysis set   |     | x              |
| Figure 14.2.5.1.2 Schirmer I test Mean change from baseline (±SEM) at each timepoint. Full analysis set                                   |     | x              |
| Figure 14.2.5.1.3 Observed percentage of patients with Schirmer I test >10mm/5min at each timepoint. Full analysis set                    |     | x              |
| Figure 14.2.5.2.1.1 SANDE global score Observed Mean (±SEM) at each timepoint. Full analysis set  |     | x              |
| Figure 14.2.5.2.1.2 SANDE global score Mean change from baseline (±SEM) at each timepoint. Full analysis set                              |     | x              |
| Figure 14.2.5.5.1 Cornea and conjunctiva vital staining total score Observed Mean (±SEM) at each timepoint. Full analysis set             |     | x              |
| Figure 14.2.5.5.2 Cornea and conjunctiva vital staining total score Mean change from baseline (±SEM) at each timepoint. Full analysis set |     | x              |
| Figure 14.2.5.6.1 TFBUT Observed Mean (±SEM) at each timepoint. Full analysis set   |     | x              |
| Figure 14.2.5.6.2 TFBUT Mean change from baseline (±SEM) at each timepoint. Full analysis set   |     | x              |

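### The tipping-point grid (Δ from 0 to -10) moves imputed SANDE scores in cenegermin's favour, so followed as written it cannot show that a SANDE result is fragile

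*SAP*

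**What the plan says.** SAP 10.1.3 plans a tipping-point analysis "for assessment of superiority (if shown) of rhNGF for each endpoint". Its purpose is that "the imputed values for the rhNGF arm are shifted by a constant to represent a worse effect in each iteration". Protocol 9.4.3.2 has the same aim, a procedure "where the imputed values for the cenegermin arm are shifted at a constant" that stands for a worse effect, but gives no sign or range.

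The SAP then prints one numeric outline: "Assuming that the tipping point is between -10 and 0, the following actions will be performed for" Δ = 0, -0.1, -0.2, down to -10. At each step Δ is added to the imputed cenegermin values and the completed data sets are re-analysed. P-values are plotted over -10 to 0, and an approximate tipping point is read off "considering a threshold for the p-values of 0.02500". A finer search follows within ±1 of that value. No separate outline is given for SANDE, although a SANDE result is planned: Table 14.2.2.4 in SAP 15.1 and "Figure 14.2.3.6 Tipping point plot SANDE. Full analysis set" in SAP 15.3.

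**The concern.** A tipping-point analysis must push the imputed active-arm values towards harm. Which sign does that depends on the scale. For Schirmer I (response is a value above 10 mm/5min) a negative shift is harmful, so the grid is right. For SANDE a negative shift is a benefit.

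Both co-primary hypotheses must be rejected to claim superiority. SANDE is read at week 12, eight weeks after treatment ends. This analysis is the planned test of how far the missing-data assumption can fail before the SANDE result is lost. Run as printed, it answers a different question and always returns reassurance.

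**Working it through.** **Direction, from the documents**

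1. SAP 12.2: both SANDE lines are 100 mm, measured left to right, from rare to constant and from very mild to very severe. The global score is the square root of frequency × severity. Higher is worse.
2. SAP 10.1.2.2: the variable imputed is the global SANDE score. The code in SAP 15.4.2 imputes AVAL and only then sets CHG = AVAL - BASE.
3. SAP 12.1, Table 3: change is post-baseline minus baseline, so a negative change is improvement.
4. Adding Δ < 0 to an imputed AVAL therefore lowers CHG for that cenegermin patient, which is an improvement.

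**The plan's own figure first**

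SAP section 5 assumes a 10-point benefit, SD 12, 72 evaluable patients (36 per arm) and one-sided alpha 0.025, and states 94.1% power for SANDE.

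- SE = 12 × √(2/36) = 2.828.
- 10/2.828 - 1.960 = 1.576, giving 94.2% power (93.7% with the noncentral t). The stated figure is reproduced, and the same SD and n are used below.

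**Shift model**

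Let b be the observed benefit at Δ = 0 (vehicle minus cenegermin mean change), m the share of cenegermin values imputed and n the number per arm.

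- Benefit after the shift: b - mΔ
- SE: √{[2 × 12² + m(1 - m)Δ²]/n}
- One-sided t test on 2n - 2 degrees of freedom

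At n = 36 and Δ = 0 the critical benefit is 1.994 × 2.828 = 5.641. The documents give neither b nor m at week 12, so both are assumed.

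Worked case, b = 6, m = 0.10:

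| Δ | Benefit | SE | One-sided p |
|---|---|---|---|
| -10 | 7.0 | 2.872 | 0.0087 |
| 0 | 6.0 | 2.828 | 0.0187 |
| +10 | 5.0 | 2.872 | 0.0431 |

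Δ at which p reaches 0.025, n = 36:

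| b | m = 0.05 | m = 0.10 | m = 0.20 |
|---|---|---|---|
| 6 | +6.8 | +3.5 | +1.8 |
| 7 | not listed | +12.3 | +6.5 |
| 10 | not listed | +34.1 | +19.1 |

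Every one is positive. In this model, for b from 5.7 to 15 and m from 2% to 30%, p on the printed grid never exceeds its value at Δ = 0.

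With n = 40 per arm (the approximate randomised number), b = 6 and m = 0.10, the tip moves to about +6.3.

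**Simulation with multiple imputation and Rubin's rules**

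Both simulations use 40 per arm and SD 12. Counts are among trials significant at Δ = 0.

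| Setting | Tips on 0 to -10 | Tips on 0 to +10 |
|---|---|---|
| Own-arm imputation, 10% missing, true benefit 6 | 0 of 830 | 213 (25.7%) |
| Same, true benefit 8 | 0 of 1216 | 168 (13.8%) |
| Same, true benefit 10 | 0 of 1403 | 85 (6.1%) |
| Reference-based imputation with ANCOVA, true benefit 7, 5% missing | 0 of 530 | 69 (13.0%) |
| Same, 10% missing | 0 of 453 | 140 (30.9%) |
| Same, 20% missing | 0 of 347 | 245 (70.6%) |

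The first three rows use 1,500 trials each with an unadjusted comparison; the last three use 800 each. Neither simulation reproduces imputation from retrieved dropouts exactly.

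**The case against.** The strongest reply is that the intent is already right: both documents ask for a worse effect, and a programmer who follows the purpose rather than the printed numbers would reverse the sign. SAP 10.1.1 also words the SANDE hypothesis as a reduction ("the change from baseline (reduction) in the global SANDE score at week 12 in cenegermin is lower or equal than control"). On that scale larger is better and a negative shift would be harmful. The code in SAP 15.4 covers only the primary analysis, so the shifted variable has to be inferred.

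The inference is nonetheless firm. SAP 10.1.3 shifts the data sets already completed by the primary imputation, and those hold the raw score. No reduction score is imputed anywhere. Because no tipping-point code is given, the text is the only specification. Correcting the sign after unblinding would be an unplanned change to a robustness check. The ±1 refinement does not help, since it starts only once a tipping point has been seen on the 0 to -10 plot.

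Three parts of the reply stand:

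- The consequence is limited. The primary test is untouched. Imputation under missing at random, complete cases and the per-protocol set also examine SANDE, though none applies progressively worse outcomes. The p-value plot would fall visibly, which could alert a reader, but the plan has no rule for that case.
- The sizes are illustrative. A benefit of 6 is chosen as borderline, and 36 per arm is already net of the 10% not evaluable. At the planned 10-point benefit, neither sign tips within 10 points in the analytic cases shown.
- The width is partly a matter of judgement. Ten points equals the planned SANDE effect, so finding no tip within +10 would still be informative.

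**Conclusion.** The concern holds. For SANDE the printed grid contradicts its stated aim and cannot find a tipping point. The sign follows from the SAP's scoring and change definitions and needs no outside assumption.

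The practical size depends on the observed benefit and the share of cenegermin values imputed. For weaker significant results the sign decides the answer: tips at +1.8 to +6.8 for a benefit of 6 with 20% to 5% imputed. For stronger results the 10-point width matters as well. This should be fixed, but it does not threaten the primary SANDE test, and the Schirmer sign is correct.

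**What to change.** In SAP 10.1.3:

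- Keep Δ = 0 to -10 for Schirmer I.
- Give SANDE its own grid: add Δ = 0, +0.1, +0.2 and so on to the imputed cenegermin scores until the one-sided p-value reaches 0.025 or a stated plausible limit, such as the scale maximum, is met.
- Define the tipping point for both endpoints as the smallest absolute Δ with p ≥ 0.025. On a negative grid the present wording, smallest Δ, literally picks the most negative value.
- If none is found, report that there was none up to the stated limit.

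As a clarification of notation only, state the SANDE hypotheses and the tested tail in SAP 10.1.1 on the scale of CHG = AVAL - BASE, where benefit is a negative cenegermin-minus-vehicle difference. Protocol 9.4.3.1 lacks the reduction wording, and the code names no tail.

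The cost is SAP and program wording before database lock and a longer computing loop for SANDE. No new data, visits or patients are needed.
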